9.1.1 Safety evaluations

Treatment safety will be monitored separately according to guidelines described in Section 15.5.2, and using the definitions of unacceptable and DLT provided in Section 9.1.2.

9.1.2 Toxicity Definitions

Toxicities will be graded according to the National Cancer Institute (NCI) Common Terminology Criteria for Adverse Events (CTCAE) version 5 criteria.

9.1.2.1 Definition of Unacceptable Toxicity

Any \geq Grade 3 AEs will be considered as unacceptable toxicities if they are possibly, probably, or definitely attributable to the protocol treatment regimen, and they occur within 30 days of vaccination. Specifically, any \geq Grade 3 organ toxicity (cardiac, renal, hepatic), including CRS-related toxicities such as hypotension and tachycardia, of any duration will be considered an unacceptable toxicity. A Grade 3 neurologic toxicity will only be declared an unacceptable toxicity if not reversible within 48 hours. Grade 3 flu-like symptoms, fever, and chills/rigors are not considered unacceptable if the duration is less than 72 hours.

Exceptions based on the disease population are as follows, with or without treatment:

- Seizures: Due to the nature of the disease under investigation in this protocol, patients may have preexisting seizures or be susceptible to new seizures as a result of the underlying disease process. Although seizures may be defined as grade 3 or 4 toxicities under NCI CTCAE, and will be reported as such in this protocol, seizures will not be considered a DLT if, in the opinion of the PI, they

have not increased in frequency or can be attributed to another recognized cause of increasing seizure frequency such as sub-therapeutic anticonvulsant levels or biopsy-proven tumor progression.

- New neurologic deficits: Due to the nature of the disease under investigation in this protocol, patients may develop new neurologic deficits as a result of tumor invasion or inflammation. A new neurologic deficit or worsening of a known neurologic deficit, which resolves (i.e. returns to baseline) within 3 weeks after initiation of medical therapy (e.g. corticosteroids) will not be considered an unacceptable toxicity.
- Thromboembolism: Due to the high incidence of deep vein thrombosis (DVT) in this patient population, patients may have undiagnosed preexisting DVTs or be susceptible to the development of DVTs due to the underlying disease process. Although DVT may be defined as a grade 3 or 4 toxicity under NCI CTCAE, and will be reported as such in this protocol, DVT will not be considered unacceptable in this protocol.
- Syndrome of inappropriate antidiuretic hormone (SIADH): Due to the high incidence of SIADH in this patient population, patients may be susceptible to the development of SIADH due to the underlying disease process. Although SIADH may be defined as grade 3 toxicity under NCI CTCAE, and will be reported as such in this protocol, SIADH will not be considered an unacceptable toxicity in this protocol unless it is refractory to medical management.
- Muscle weakness and weight gain: Due to the high incidence of generalized muscle weakness (i.e. steroid myopathy) and weight gain in patients taking steroids in this patient population, patients may be susceptible to the development of generalized muscle weakness or weight gain, which is due to steroids alone. Although generalized muscle weakness may be defined as grade 3 or grade 4 toxicity and weight gain $\geq 20\%$ may be defined as grade 3 toxicity under NCI CTCAE, and will be reported as such in this protocol, generalized muscle weakness or weight gain will not be considered an unacceptable toxicity in this protocol if the patient has required steroids greater than the physiologic doses in the interval between the immunization and the development of the toxicity.
- Tumor progression: Due to the nature of the disease under investigation in this protocol, patients may have an increase in preexisting neurologic deficits or have an onset of new neurologic deficits due to tumor progression. Although such neurologic deficits may be defined as AEs under NCI CTCAE, these clinical changes could be an expected phenomenon in this disease due to tumor growth. As a result, neurologic deficits will not be considered unacceptable toxicities if unequivocal tumor progression can be documented radiographically or histologically.

Unacceptable \geq Grade 3 Toxicity

Any \geq Grade 3 organ toxicity (cardiac, renal, hepatic), including CRS-related toxicities such as hypotension and tachycardia, of any duration that is attributable to vaccination will be considered an unacceptable toxicity. Please see Section

9.1.4 for guidelines on management of immune response, including CRS. Patients will be monitored for 30 days after each vaccine. As vaccines #1 through #5 are close in proximity (priming phase of vaccination), patients will be monitored from vaccine #1 until 30 days after vaccine #5.

Patients will also be monitored for 30 days after vaccine 6 and vaccine 7 (booster phase of vaccination). Toxicities must occur within this 30-day period to be considered an unacceptable toxicity attributable to vaccination.

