9.1.2.2 Definition of Dose Limiting Toxicity (DLT)

As defined in Section 9.1.2.1, a DLT is as an unacceptable toxicity that occurs during the DLT observation period that extends between vaccine #1 and 30 days after vaccine #5.

Patients receiving less than 5 vaccines without experiencing a DLT will be replaced in the decision-making concerning dose escalation.

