12.6 Study Assessments

12.6.1 Medical History

Medical history will be obtained from the Duke electronic system and from the subject and/or family at the screening visit and reviewed at each study visit. This data may include the following:

- All past medical and surgical history;
- Current medications;

- Changes in physical or neurologic symptoms;
- Any AEs.

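### The seizure exception tests frequency alone, so in a patient with preexisting seizures a vaccine-attributed Grade 4 or prolonged Grade 3 seizure can leave the DLT count

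*Combined protocol and SAP*

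**What the plan says.** The base rule in Section 9.1.2.1 is that Grade 3 or higher "AEs will be considered as unacceptable toxicities if they are possibly, probably, or definitely attributable to the protocol treatment regimen" and fall within 30 days of vaccination. One general limit applies to neurologic events: "A Grade 3 neurologic toxicity will only be declared an unacceptable toxicity if not reversible within 48 hours".

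A list of exceptions tied to the disease population follows. The seizure exception begins "Although seizures may be defined as grade 3 or 4 toxicities under NCI CTCAE, and will be reported as such in this protocol". It then takes such events out of the DLT count, on the PI's judgement, where the seizures "have not increased in frequency or can be attributed to another recognized cause of increasing seizure frequency such as sub-therapeutic anticonvulsant levels" (biopsy-proven progression is the second example of another cause).

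Section 9.1.2.2 builds the DLT on this definition: "a DLT is as an unacceptable toxicity that occurs during the DLT observation period that extends between vaccine #1 and 30 days after vaccine #5". Section 8 makes the percentage of patients with a DLT, by stratum and dose level, the primary endpoint. Section 15.5.1.1 uses the count in a 3+3 rule: 0/3 or 1/6 clears a dose, 1/3 adds three patients at the same level, and 2 of 3 or 2 of 6 sends the next cohort to a lower dose.

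**The concern.** The exceptions exist so that events expected from the tumor are not charged to the vaccine. The seizure exception goes further. Its two alternatives are joined by an *or*, so unchanged frequency is enough by itself, whatever the grade, duration or attribution. Take a patient with regular mild seizures who has one life-threatening seizure soon after a vaccine, judged definitely related. If the PI finds that seizures are no more frequent than before, the event is not a DLT. PI judgement does not cure this, because the question put to the PI is frequency.

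At stake is the count that decides whether 300 or 400 µg/peptide/dose is declared tolerable in each CMV stratum, with three or six patients per decision. The events that can be lost are the more severe seizures, because the short Grade 3 ones are already excluded by another rule.

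**Working it through.** **Step 1. Which seizures does the exception remove that would otherwise count?** All are taken as attributable and inside the DLT window.

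| Seizure | Base and 48-hour rules | After the exception, frequency unchanged |
|---|---|---|
| Grade 3, reversible within 48 hours | Not counted | Not counted |
| Grade 3, not reversible within 48 hours | Counted | Not a DLT |
| Grade 4, any duration | Counted (the 48-hour rule names Grade 3 only) | Not a DLT |
| First seizure in a patient with none before | Counted if Grade 4 or prolonged Grade 3 | Still counted: frequency has risen, unless another cause is recognized |

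The added effect is confined to rows two and three, in patients with preexisting seizures.

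**Step 2. Does another rule put the event back?**
- The any-duration rule covers "organ toxicity (cardiac, renal, hepatic), including CRS-related toxicities such as hypotension and tachycardia, of any duration that is attributable to vaccination". Seizures are not listed.
- Section 9.1.4 withholds that patient's next treatment after a Grade 3 or higher toxicity not explained by other causes. It does not govern DLT counting.
- The second alternative in the seizure exception is also framed around rising frequency and adds no severity test.

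None restores the event to the DLT count.

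**Step 3. Is the comparator defined?** No look-back period is given. Section 12.6.1 takes past medical history, and history that may include "Changes in physical or neurologic symptoms", at screening and each visit. Table 3 schedules neurologic examinations. Neither names a seizure count or worst grade, and adverse event recording starts at vaccine #1 (Section 13.1).

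**Step 4. Effect on one decision** (Section 15.5.1.1). One exempted patient turns 1/3 (three more patients at the same level) into 0/3 (dose cleared), or 2/6 (lower dose) into 1/6 (dose cleared).

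**Step 5. Effect on the chance of clearing a dose.** The plan states no operating characteristic for the 3+3 rule, so there is no figure to reproduce. With independent patients and counted DLT probability p,

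P(clear) = (1−p)³ + 3p(1−p)² × (1−p)³.

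The first term is 0/3; the second is 1/3 followed by 0/3.

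- p = 0.30: 0.3430 + 0.1513 = 0.494
- p = 0.29: 0.3579 + 0.1570 = 0.515
- p = 0.25: 0.4219 + 0.1780 = 0.600
- p = 0.20: 0.5120 + 0.1966 = 0.709

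Both the true rate and the points lost (patients whose only DLT is an exempted seizure) are assumptions.

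| True DLT rate | None lost | 1 point lost | 5 points lost | 10 points lost |
|---|---|---|---|---|
| 20% | 0.709 | 0.730 | 0.814 | 0.906 |
| 30% | 0.494 | 0.515 | 0.600 | 0.709 |
| 40% | 0.309 | 0.326 | 0.396 | 0.494 |

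**Step 6. Table 4.** The seizure exception speaks of a DLT, whereas the Section 15.5.2 suspension thresholds count unacceptable toxicities. Read literally, an exempted seizure is still an unacceptable toxicity and counts in Table 4. Read through Section 9.1.2.2, where a DLT is simply an unacceptable toxicity within the window, it counts in neither. The text does not settle which.

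**The case against.** The strongest reply is that the clause is a deliberate allowance for background seizures, that it bites rarely, and that other oversight remains. To be lost, a seizure must be Grade 4 or prolonged Grade 3, attributable to the regimen, in a patient with preexisting seizures, without a rise in frequency, and inside the DLT window. Exempted seizures are still reported as adverse events. The PI reviews events weekly (Section 13.1.1), an unexpected frequency of Grade 3 or 4 events can lead to de-escalation or closure (Section 14.1), the safety oversight committee sees all toxicities by maximum grade (Section 15.5.3), and a possibly related death suspends accrual (Section 15.5.2). All of this stands and limits the harm. None of it changes the DLT count.

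Four stronger readings are tempting, and the documents do not support them:
- *Only the seizure exception lacks a severity or recovery condition.* Of the five others, only new neurologic deficits and SIADH have a recovery or refractoriness test. DVT has no condition, and muscle weakness or weight gain and tumor progression have cause conditions. The 72-hour limit for flu-like symptoms belongs to the base rule.
- *Preexisting seizures are frequent here, so many DLTs are lost.* Section 9.1.2.1 says only that patients may have them. A loss of 10 points at a true rate of 30% would make one third of all DLTs exempted seizures, which nothing in the documents supports.
- *Baseline seizure data are not collected.* History and neurologic examinations are taken, and the protocol does not list eCRF fields. What can be said is that no specific item or look-back is defined.
- *Exempted seizures escape all stopping rules.* Whether they count in Table 4 is unclear, not settled.

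It is also fair that patients have already been treated under the present wording, so a change is not free.

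**Conclusion.** The point holds in this form: the frequency alternative conflicts with the base rule on attributable Grade 3 or higher events. Followed as written, it drops a vaccine-attributed Grade 4 or prolonged Grade 3 seizure from the primary endpoint when a patient with preexisting seizures has no more of them than before. That rests on the text and not on any rate.

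The size is uncertain. A single event can change a cohort decision. Across cohorts, at a true DLT rate of 30%, the rise in the chance of clearing a dose is about 0.02 (0.515 − 0.494) if 1 point is lost, 0.11 (0.600 − 0.494) if 5 are, and 0.21 (0.709 − 0.494) if 10 are. These assume independent patients and a common rate. With no seizure rate in the documents, no value in the range can be preferred, and the upper end should not be read as an estimate. The change is worth making because it is small and concerns the most severe seizures.

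**What to change.** - **Reconcile the exception with the base rule in Section 9.1.2.1**, so that unchanged frequency alone does not exempt an attributable seizure that is worse in CTCAE grade than the patient's baseline. One way is to require no increase in either frequency or CTCAE grade. Leave the alternative-cause limb as it is. The final criterion is for the sponsor to decide.
- **State whether an exempted seizure counts as an unacceptable toxicity for Table 4**, and use the same term in both places.
- **Record seizure frequency and worst grade before vaccine #1** as a specific item at final screening, over a stated look-back period.
- **Re-check patients already treated** against the revised wording, using existing adverse event and history records. Section 10.1.4 reports the first six treated and a second six under DLT observation as of 24 April 2024.

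The cost is a short wording change, a sentence on Table 4, one eCRF item and a one-time record review. There are two drawbacks. An occasional severe seizure of uncertain cause will count as a DLT, which is slightly conservative for escalation. Baseline data for patients already treated will be retrospective, so the report should say which patients were assessed that way.

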10.2 Hiltonol®

10.2.1 Names, Classification, and Mechanism of Action

Carboxymethylcellulose, poly (I:C), and poly-L-lysine double-stranded RNA (poly-ICLC) (Hiltonol®) will be administered 1) in conjunction with P30-EPS peptides on Days 1, 4, 8, 15, and 22 of the Priming Phase, 2) in conjunction with P30-EPS peptides on Days 84 and 140 of the Booster Phase, and 3) will be given alone (at home) on Days 98, 112, and 126 of the Booster Phase (i.e., every 2 weeks between vaccines 6 and 7). Hiltonol® will be provided by Oncovir.

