12.5.2 Follow-up Requirements for Early Withdrawal

All patients who receive a vaccine will be followed for PFS and survival (please see Section 15.6.5) until death or loss to follow-up. Subjects will also be assessed and followed for SAE monitoring/safety analysis for 30 days following the last vaccine injection.

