13.1 AEs

An AE (AE) is any untoward medical occurrence in a subject receiving study drug and which does not necessarily have a causal relationship with this treatment. For this protocol, the definition of AE also includes worsening of any pre-existing medical condition. An AE can therefore be any unfavorable and unintended or worsening sign (including an abnormal laboratory finding), symptom, or disease temporally associated with the use of study drug (i.e., bevacizumab or vaccine), whether or not related to use of the study drug(s).

From the time the subject receives vaccine 1 through the End of Study visit (as defined in Section 12.4), all AEs must be recorded in the subject medical record and AEs case report form.

AEs will be assessed according to the CTCAE version 5. If CTCAE grading does not exist for an AE, the severity of the AE will be graded as mild (1), moderate (2), severe (3), life-threatening (4), or fatal (5).

Attribution of AEs will be indicated as follows:

- Definite: The AE is clearly related to the study drug(s)
- Probably: The AE is likely related to the study drug(s)
- Possible: The AE may be related to the study drug(s)
- Unlikely: The AE is doubtfully related to the study drug(s)
- Unrelated: The AE is clearly NOT related to the study drug(s).

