15.5.2 Overall Toxicity Monitoring Guidelines

With vaccinations potentially being administered through day 140, we will be monitoring within each stratum for the occurrence of unacceptable toxicities throughout vaccine treatment.

Tabulated below ([Table 4](#)) are the conditions under which accrual to a stratum will be temporarily suspended and data carefully reviewed to determine if accrual should be continued or terminated, and whether elements of the treatment regimen should be modified. Accrual will also be suspended whenever a death occurs that is possibly, probably, or definitely related to vaccine treatment.

Table 4: Conditions for Temporary Accrual Suspension

Number of Patients Within CMV Stratum Treated at a Particular Dose Level	Number of patients with unacceptable toxicity
0-6	≥2
7-9	≥3
10-14	≥4
≥15	≥5

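### At nominal timing, non-fatal Grade 3-4 events on Days 115-139, including reactions to the Day 126 home Hiltonol injection, do not count toward the Table 4 accrual-suspension rule

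*Combined protocol and SAP*

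**What the plan says.** - **Definition.** Section 9.1.2.1 treats Grade 3 or higher AEs as unacceptable, subject to listed exceptions, if they are at least possibly "attributable to the protocol treatment regimen, and they occur within 30 days of vaccination". For the booster phase it sets 30 days of monitoring after vaccine #6 and after vaccine #7, then adds: "Toxicities must occur within this 30-day period to be considered an unacceptable toxicity attributable to vaccination".
- **Treatment between those vaccines.** Section 10.2.1 states that Hiltonol "will be given alone (at home) on Days 98, 112, and 126 of the Booster Phase".
- **Monitoring rule.** Section 15.5.2 states that "we will be monitoring within each stratum for the occurrence of unacceptable toxicities throughout vaccine treatment". Table 4 then suspends accrual to a stratum at 2 or more patients with unacceptable toxicity among up to 6 treated at a dose level, 3 or more among 7-9, 4 or more among 10-14, and 5 or more from 15 upward. Section 5.5 likewise presents these rules as directed at the whole of treatment. Section 15.5.2 also suspends accrual for any treatment-related death and sets no time limit on that trigger.
- **Related text.** Section 13.1 defines an AE by reference to "use of study drug (i.e., bevacizumab or vaccine", with Hiltonol given alone not listed. Under Section 12.5.2, early withdrawals are "followed for SAE monitoring/safety analysis for 30 days following the last vaccine injection", whereas Section 12.3 counts 30 days from the final treatment intervention.

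**The concern.** Section 9.1.2.1 attributes toxicity to the whole regimen, so a reaction to Hiltonol given alone passes the attribution test. It fails only on the calendar, because the home injections do not open a window of their own. The documents give no reason for leaving those days out, and the description in Section 15.5.2 would lead a reader to think they are included.

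Table 4 is the only numeric accrual trigger that covers the booster phase, and in a stratum with up to six patients at a dose level it turns on two patients. The self-administered injections are also given away from clinic observation. At stake is whether related events in the later part of the home-injection period can prompt the review that Table 4 is meant to prompt.

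**Working it through.** **Inputs.** Vaccine #5 on Day 22, vaccine #6 on Day 84 ±7, vaccine #7 on Day 140 ±7 (Section 9.1); a 30-day window anchored on vaccines (Section 9.1.2.1); home Hiltonol every 14 days (Section 10.2.1); thresholds from Table 4.

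**1. The plan's own home-injection days.** 84 + 14 = 98; 84 + 28 = 112; 84 + 42 = 126. These reproduce Section 10.2.1.

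**2. Nominal gap.** The vaccine #6 window closes on Day 84 + 30 = 114 and the next opens on Day 140. Uncovered: Days 115-139, that is 139 − 115 + 1 = 25 days. Day 98 is inside the window. Day 112 is inside, with 114 − 112 = 2 further covered days. Day 126 is outside.

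**3. Gap across the visit windows.** First uncovered day = vaccine #6 day + 31; last = vaccine #7 day − 1; third home injection = vaccine #6 day + 42.

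| Vaccine #6 | Vaccine #7 | Uncovered days | Length | Third home injection |
|---|---|---|---|---|
| 77 | 133 | 108-132 | 25 | 119, in gap |
| 77 | 140 | 108-139 | 32 | 119, in gap |
| 77 | 147 | 108-146 | 39 | 119, in gap |
| 84 | 133 | 115-132 | 18 | 126, in gap |
| 84 | 140 | 115-139 | 25 | 126, in gap |
| 84 | 147 | 115-146 | 32 | 126, in gap |
| 91 | 133 | 122-132 | 11 | would coincide with vaccine #7 |
| 91 | 140 | 122-139 | 18 | 133, in gap |
| 91 | 147 | 122-146 | 25 | 133, in gap |

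The third injection falls 42 days after vaccine #6 at 14-day spacing, and 3 × 12 = 36 days after it if each interval is shortened by 2 days. Both exceed 30, so its exclusion does not depend on where vaccine #6 lands.

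**4. The earlier gap.** The priming window closes on Day 22 + 30 = 52. Days 53-83 are uncovered: 83 − 53 + 1 = 31 days, with no protocol injection among them.

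**5. Effect on the count.** Suppose two of six patients had related, otherwise qualifying Grade 3 events on Day 127. Since 127 − 84 = 43 > 30, Table 4 scores 0 of 6 against a threshold of 2.

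**6. Illustration with assumed rates.** The documents give no toxicity rates and no operating characteristics for Table 4. Assume 10% of patients have a counted event and a further 5-15% have a qualifying event only in the gap. For n = 6 the chance of reaching the threshold is 1 − (1 − p)^6 − 6p(1 − p)^5:
- p = 0.10 (as written): 1 − 0.531 − 0.354 = 0.11
- p = 0.15: 0.22
- p = 0.20: 0.34
- p = 0.25: 0.47

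For n = 14 with threshold 4, the same comparison gives 0.04 as written against 0.15 to 0.48.

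**7. Follow-up text.** For a patient who takes the Day 126 injection and withdraws before vaccine #7, Section 12.5.2 ends SAE follow-up on Day 114, before that injection. Applying the Section 12.3 rule, with that injection as the final intervention, would give 126 + 30 = Day 156.

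**The case against.** A reader might infer that Grade 3 or higher reactions to home Hiltonol can never suspend accrual, or that the trial's safety summaries understate toxicity. The documents support neither. Grade 5 is covered by the related-death trigger, which has no window (although Section 15.5.2 does not say whether its reference to vaccine treatment includes Hiltonol alone). The AE tabulations in Section 15.5.3 have no 30-day limit and include everyone given a first vaccine. The DLT endpoint (Section 9.1.2.2) and the MTD rule (Section 15.5.1.1) use the priming window only.

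Nor are gap events unwatched. AEs are recorded from vaccine #1 to end of study (Section 13.1) and reviewed weekly (Section 13.1.1). A Grade 3 or higher event can hold that patient's next treatment (Section 9.1.4). Section 14.1 lets the investigator act on an excess of severe events. All of this stands, but none of it is a numeric accrual trigger, so it does not replace Table 4.

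The exposure affected is limited. One of the three planned home injections falls in the gap. The reactions described in Section 7.2.2 were early, typically 2-4 hours after vaccination in the related pp65 trial and usually limited to 48 hours in an earlier poly-ICLC glioma trial, so two covered days after Day 112 span that period. Grade 3 flu-like symptoms, fever and chills lasting under 72 hours are exempt at any time.

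Finally, the wording is not airtight. Section 15.5.2 may only mean to contrast with the acute period, using a term that Section 9.1.2.1 has already limited, and Section 10.2.2 loosely calls a home injection a vaccination. But Section 9.1.2.1 names vaccines #6 and #7 as its booster anchors, and a suspension rule open to two readings needs clarifying anyway.

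**Conclusion.** The point holds in a bounded form. On the plain reading of Section 9.1.2.1, non-fatal Grade 3-4 events attributable to the regimen do not count toward Table 4 on 25 days between vaccines #6 and #7 at nominal timing (11 to 39 days across the visit windows), and these days include the third home injection. This does not match how Sections 15.5.2 and 5.5 describe the rule. The inconsistency concerns one monitoring trigger, which leads to temporary suspension and review; it does not reach the primary endpoint or the AE reporting.

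The conclusion assumes that home Hiltonol is not itself a vaccination for the purpose of the window. The day counts are exact for the stated schedule. The probabilities rest on assumed rates and show direction only. The Section 12.5.2 and 13.1 points are secondary: the first is a mismatch in SAE follow-up for early withdrawals, and the second loses no event by itself, since Hiltonol is listed among the study drugs in Section 10.

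**What to change.** 1. Reconcile Section 9.1.2.1 with Sections 15.5.2 and 5.5 **for the Table 4 count only**. State that Grade 3 or higher events attributable to the regimen and meeting the other criteria count from vaccine #1 through 30 days after the last protocol injection, whether vaccine or Hiltonol alone. For a patient on the nominal schedule this leaves no uncovered day through Day 140 + 30 = 170. Giving each home injection its own 30-day window (98-128, 112-142, 126-156) would also close Days 115-139, but would leave Days 53-83 open.
2. Say explicitly that the DLT window and the criteria for an individual patient to continue treatment are unchanged. Sections 9.1 and 9.1.6 use unacceptable toxicity for continuation, so a general rewording of Section 9.1.2.1 would reach further than intended.
3. Reconcile Section 12.5.2 with Section 12.3 on the start of the 30-day SAE follow-up, and name Hiltonol in the study-drug parenthesis of Section 13.1.

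**Cost.** Amendment wording; no new data are needed because these events are already recorded. A few more events may count toward Table 4, so temporary suspension and review may occur slightly more often.
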